## 4.3.4 Immunogenicity Set

The Immunogenicity Set consists of all subjects from the Safety Set and who have at least one immunogenicity measurement taken.

## 4.3.5 PK Analysis Set

The PK Analysis Set consists of all subjects who have been exposed to GEN1029 (i.e. at least one dose of IMP) and who have at least 1 post-dose PK measurement. PK parameters like Cmax, AUC, ... at Cycle 1 Day 1 will be considered as post-baseline measurements as in the calculation post-baseline and baseline (pre-dose) concentrations are included.

## 4.4 Subgroup Definitions

If at least 5 subjects per subgroup per dose level are available, subgroup analyses by ADA-positivity are planned.

Other sub-group analyses may be performed post-hoc. Due to the low expected number of subjects per site no investigation of site effects is planned.

## 4.5 Treatment Assignment and Treatment Arms

Data will be grouped according to treatment dose level in the biweekly regimen, as described below, rather than by 'treatment arm'. Intensified and Priming regimen only have 1 subject per regimen and will be provided only in listings (cf. section 3.3).

In biweekly regimen, subjects will receive one infusion of GEN1029 every second week. The following doses are planned: 0.1 mg/kg, 0.2 mg/kg, 0.3 mg/kg, 1.0 mg/kg, 2.0 mg/kg and 3.0 mg/kg. Other dose levels were planned in the protocol v9.0, as the MTD was identified, those were not investigated.

Results will be grouped according to dose-level and total.

All data will be listed by dose level, subject ID (subject treatment number), site ID and visit (if applicable). Data related to screen failures will be listed by screening number.

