Based on nonclinical and clinical data available to date, and published data from other human DR5 mAbs, the conduct of the trial GCT1029-01 is regarded as justifiable. Furthermore, the patient population eligible for the current trial is patients with selected advanced and/or metastatic cancer, who have failed available standard therapy or who are not candidates for standard therapy, and for whom in the opinion of the investigator, experimental therapy with GEN1029 may be beneficial. All patients enrolled in this trial will be controlled frequently by qualified health care professional(s) who will provide care and closely monitor and evaluate the patient's response to the trial drug, in terms of its safety and efficacy.

As of the 20-Aug-2019, 27 patients have been exposed to GEN1029 at dose levels ranging from 0.3 to 3 mg/kg: 24 patients on the Biweekly Regimen (Q2W) and 3 patients on the Intensified Regimen ($8 \times Q1W/Q2W$). Based on this experience, two AEs have been identified as risks and AEs of special interest (AESIs). These are elevated transaminase levels and diarrhea (Section 10.3). As a result, a mitigation plan for handling AEs of diarrhea has been prepared for this trial to guide diagnostic steps and treatment.

Of note, all 3 patients exposed in the Intensified Regimen experienced DLTs due to transaminase elevations,

Consequently, the Intensified

Regimen is permanently discontinued.

More detailed information about the known and expected benefits and risks including reasonably expected AEs of GEN1029 can be found in the Investigator's Brochure.

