4.5 Planned Number of Patients

The dose escalation part will enroll up to approximately 100 patients shared between the Biweekly and Priming Regimens. Three patients were exposed in an Intensified Regimen (8xQ1W/Q2W) all of whom experienced DLTs and, consequently, this dosing regimen was permanently discontinued.

In the expansion part, the planned number of patients depends on how many indications and regimens that will be evaluated. Each opened cohort (which is indication and regimen specific) will enroll between 10 and 60 patients. Opening all seven cohorts would allocate between 70 (minimum 10 in each) and 420 (maximum 60 in each) patients in the expansion part.

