6.4.1 Prophylactic Concomitant Medication

Fourteen out of 27 patients (11 out of 24 patients in the Biweekly Regimen and 3 out of 3 patients in the Intensified Regimen) have experienced transaminase elevations \geq grade 2. These elevations seem to be primarily a first-dose effect, and independent of dose level or presence of liver metastasis. Preliminary data from the ongoing dose escalation suggests that pre-medication with steroids may prevent elevations of transaminases.

Therefore, mandatory pre-medication with Dexamethasone must be administered as follows:

- 4 mg/p.o. one day before dosing at Cycles 1 and 2.
- Dose escalation part: 10 mg. i.v. at Day 1 before dosing and at Day 2 in Cycles 1 and 2. Expansion part: 10 mg. i.v. at Day 1 before dosing and orally at Day 2 in Cycles 1 and 2.

If a drug-related \geq grade 2 elevation of ALT and/or AST is observed during the second cycle or thereafter, dexamethasone pre-medication should be continued/re-introduced. In this case, Dexamethasone can be given orally on the day after the dosing day.

Furthermore, the below guidance should be followed throughout the trial:

• Paracetamol (Acetaminophen) and antihistamines (Diphenhydramine, 50 mg p.o. preferred, or Dexchlorpheniramine (5 mg i.v.), can be part of the pre-medication regimen as judged necessary by the investigator.

All pre-medication must be reported on the concomitant medication page in the eCRF.

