## 3.3 Sample Size Justification

The protocol v9.0 planned to enroll up to approximately 100 subjects shared between the Regimens. As the MTD was found earlier than the highest dose level planned in the protocol and the expansion will not be initiated, only 48 subjects will be recruited.

Of those 48 subjects:

Page 8 of 44

TPL N°: eTPL SA-02-01 Of SOP SA-02.08 TPL Effective Date: 31 Mar 2016

- Two subjects were assigned to the priming regimen:
- One received the priming dose and then continued on a lower dose level. This subject is considered as treated on the 'biweekly regimen'.
- The second subject received the priming dose and continued with a higher dose level, this subject will be analysed as treated in the priming regimen.
- Three subjects were also planned in an Intensified Regimen (8xQ1W/Q2W) all of whom experienced DLTs and, consequently, this dosing regimen was permanently discontinued.

The Intensified Regimen was discontinued per protocol v9.0.

More details on sample size can be found in section 11.8 Sample Size Calculation of the protocol final version 9.0 dated 24 October 2019.

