### 4.3.2 Safety Set

The Safety Set (SAF) consists of all subjects who received at least one dose of GEN1029. Subjects will be analyzed according to the actual trial treatment received. The FAS and the Safety Set (SAF) are defined the same way.

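### SAP 4.5 confines the Intensified Regimen to listings on a count of one subject; SAP 3.3 and the protocol give three, all with DLTs, so tables labelled Safety Set would omit dosed subjects

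*SAP*

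**What the plan says.** SAP 4.5 groups data by dose level within the biweekly regimen. On the other two regimens it says: "Intensified and Priming regimen only have 1 subject per regimen and will be provided only in listings", with a cross-reference to SAP 3.3. It then says: "Results will be grouped according to dose-level and total". It does not define the total.

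SAP 3.3 states that "only 48 subjects will be recruited". Two of these were assigned to Priming, one of whom is analysed as biweekly, which leaves one Priming subject. On the Intensified Regimen it says: "Three subjects were also planned in an Intensified Regimen (8xQ1W/Q2W) all of whom experienced DLTs".

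The protocol agrees on three. Protocol 4.5 says: "Three patients were exposed in an Intensified Regimen (8xQ1W/Q2W) all of whom experienced DLTs". Protocol 2.3 adds that "all 3 patients exposed in the Intensified Regimen experienced DLTs due to transaminase elevations". Protocol 6.4.1 counts three of three Intensified patients among those with transaminase elevation of grade 2 or higher.

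SAP 4.3.2 sets no restriction by regimen: "The Safety Set (SAF) consists of all subjects who received at least one dose of GEN1029". SAP 17 puts all safety results on that set. SAP 4.2 bases the final analysis on all dose-escalation subjects, and SAP 4.8 sends all available data to tabulations as well as listings.

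**The concern.** The count of one is the only stated ground for listing-only reporting, and the section cited for it gives a different number for one of the two regimens.

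Subjects who appear only in listings cannot be in a tabulated total. The natural reading of SAP 4.5 is therefore a biweekly-only total. Tables that SAP 21.1 labels Safety Set, such as the summary of treatment-emergent adverse events (Table 14.03.03) and the liver laboratory abnormalities (Table 14.03.37), would then not cover the Safety Set. Nor would they reconcile with the Regimen Allocation table (14.01.02.02), which is on all dosed subjects. SAP 5 does not list the exclusion among the changes to the protocol.

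Establishing the safety profile is a primary objective, and elevated transaminases are an adverse event of special interest. The three subjects are the hepatic DLT cases that led to the regimen being discontinued, so leaving them out lowers the summary rate of the toxicity of most interest.

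**Working it through.** **1. The count.**

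| Source | Intensified | Priming |
|---|---|---|
| SAP 4.5 | 1 | 1 |
| SAP 3.3 (cited by SAP 4.5) | 3 | 1 analysed as such |
| Protocol synopsis, 2.3, 4.5, 6.4.1 | 3 | – |

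The protocol's figures at 20 August 2019 are internally consistent: 24 biweekly + 3 Intensified = 27 exposed, and 11 + 3 = 14 with transaminase elevation of grade 2 or higher. The figure of one cannot be reproduced for the Intensified Regimen.

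**2. Subjects left out of a biweekly-only total.** The final Safety Set size is not stated, so it is bounded.

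- Lower bound: 27 exposed by August 2019 + 1 Priming subject, who is in neither of the two groups counted then = 28.
- Upper bound: 48 recruited, if all were dosed.
- Omitted: 3 Intensified + 1 Priming = 4, which is 4/48 = 8.3% to 4/28 = 14.3%.
- At N = 48 the tabulated total would be 48 − 4 = 44. On SAP 4.5's own counts it would be 48 − 2 = 46.

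**3. Effect on the transaminase rate, August 2019 data (protocol 6.4.1).**

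- With the Intensified subjects: 14/27 = 51.9% (Clopper-Pearson 95% CI 31.9 to 71.3).
- Without them: 11/24 = 45.8% (25.6 to 67.2).
- Gap: 6.0 points.
- The three are 3/27 = 11.1% of exposed subjects but 3/14 = 21.4% of cases.

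Protocol Table 7-1 starts grade 2 transaminase elevation above 3 × ULN. That is also the first threshold in the liver table of SAP 17.5, so that row is the one most directly affected. The exact count there may differ, because SAP 17.5 uses only central laboratory values in summary tables.

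**4. Projection to N = 48.** Let p be the biweekly rate and x = 0 or 1 the Priming subject's event. The full total is (44p + 3 + x)/48, to be compared with p.

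| Assumed p | 44p | Full total, x = 0 / 1 | Gap in points |
|---|---|---|---|
| 30% | 13.2 | 33.8% / 35.8% | 3.8 / 5.8 |
| 45.8% | 20.17 | 48.3% / 50.3% | 2.4 / 4.5 |
| 60% | 26.4 | 61.3% / 63.3% | 1.3 / 3.3 |

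**The case against.** The strongest reply is that the count of one may follow from analysis by treatment actually received. SAP 3.3 moves one Priming subject to the biweekly group on such grounds, and it describes the three Intensified subjects as planned, not as analysed in that regimen. Protocol 7.1 requires treatment to stop at a DLT, so a subject stopped after one infusion could look the same as a biweekly subject. If two of the three were moved, only two of 48 would be omitted (4.2%). The August 2019 comparison would be 14/27 against 13/26, a gap of 1.9 points. At N = 48, with a 45.8% rate in the other 44 subjects, the gap would be 0.1 to 2.2 points (22.17/46 against 23.17/48 or 24.17/48).

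Neither document says this happened. SAP 3.3 spells out the move for Priming and is silent for Intensified. SAP 4.3.3 refers to a separate analysis-populations plan that was not available here, but SAP 4.5 does not cite it. If two subjects were moved, two DLT cases would enter the biweekly dose-level columns, including the primary DLT table, and the SAP would need to say so.

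Four further points have some force.

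- Because the total is undefined, SAP 4.5 could be read as governing only separate regimen columns, with the total still covering the Safety Set. SAP 4.2 and 4.8 would fit that reading, but the restriction to listings does not.
- The cases stay visible: in the AE and DLT listings, and probably in the DLT graph of SAP 17.1, the swim-lane plots of 17.3 and the liver profiles of 17.5.
- The lower bound of 28 is unlikely to be close to the truth. SAP 4.5 includes 0.1 and 0.2 mg/kg groups, below the range dosed by August 2019.
- Listing-only display is defensible for three subjects, and pooling schedules blurs a biweekly safety profile. That bears on layout. It does not justify a total that fails to match its population label.

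**Conclusion.** The concern holds and should be fixed. The stated ground for listing-only reporting is contradicted by the section it cites and by four places in the protocol. That finding does not depend on how many of the 48 were dosed.

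The biweekly-only total is an inference, though the most natural one, from text that leaves the total undefined. If it is what is meant, four dosed subjects drop out of tables labelled Safety Set. The transaminase gap is 6.0 points on the 2019 data and 1.3 to 5.8 points at N = 48. The projection assumes that all 48 were dosed, that biweekly rates lie between 30% and 60%, and that all three Intensified subjects are analysed in that regimen.

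The damage is limited to descriptive totals. No test or decision rule uses them, and the biweekly dose-level DLT columns are unaffected unless an Intensified subject was reclassified.

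**What to change.** 1. Correct the Intensified count in SAP 4.5 to three. If any of the three is analysed under another regimen by treatment received, say so in the SAP or in the analysis-populations plan named in SAP 4.3.3.
2. Define the total in safety tables as all Safety Set subjects, shown beside a biweekly subtotal. Priming (n = 1) can stay in listings but counts in the total.
3. Add one column or short table for the three Intensified subjects covering DLTs, adverse events of special interest and liver abnormalities, kept apart from the biweekly dose-level DLT columns. This item matters less than the first two.

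The cost is SAP wording, one definition, and a column or short table. No new data are needed. The total will pool dosing schedules, which the biweekly subtotal offsets.

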## 4.6 Calculated Variables

• Baseline is defined as the available data from the latest recorded measurement made before the first IMP administration (trial day 1). Measurements done on the same date as the first IMP administration will be considered as done before the first IMP administration unless specified otherwise (i.e the time associated with the date implies that the measurement was done after the first IMP, even if it is during the same day). For PK variables, the IMP administration on Day 1 of each cycle will be time 0.

Page 11 of 44

TPL N°: eTPL SA-02-01

TPL Version: 02

Of SOP SA-02.08
TPL Effective Date: 31 Mar 2016
Approved in Vault: 07 Mar 2022

- Change from baseline is defined as the post-baseline value baseline value.
   Change from baseline will be missing when either post-baseline or baseline value is missing.
- For laboratory data, local change from baseline will be calculated as the post-baseline local value local baseline value. Local change from baseline will be missing when either local post-baseline or local baseline value is missing.
- For laboratory data, central change from baseline will be calculated as the post-baseline central value central baseline value. Central change from baseline will be missing when either central post-baseline or central baseline value is missing.
- Percent change from baseline is defined as 100\*(post-baseline value baseline value)/baseline value. If the baseline value is 0 and the post-baseline value is 0, the change from baseline and the percent change from baseline are both 0. If the baseline value is 0 and the post-baseline value is not 0, the percent change from baseline will be undefined (missing value).
- Time (in months) from first diagnosis of primary site to start date of IMP: (start date of IMP date of first diagnosis)/30.4375.
- Time (in months) since most recent recurrence/relapse or progression to start date of IMP: (start date of IMP date of most recent recurrence/relapse or progression)/30.4375.
- Time (in months) since last biopsy: (start date of IMP date of most recent biopsy)/30.4375.
- Total number of days in trial: max (last contact date, date of death) start date of IMP + 1.
- Total treatment duration (days): (end date of IMP start date IMP) +1,
   End date of IMP related to

#### Biweekly and Priming regimen:

• min (last IMP+13a, last contact date, cut-off date)

#### • Intensified Regimen:

- min (last IMP+6b, last contact date, cut-off date) up to Cycle 4 included
- min (last IMP+13, last contact date, cut-off date) after cycle 4
- Actual cumulative dose (mg): sum of all actual doses administered.

Approved in Vault: 07 Mar 2022

- Dose intensity (mg/cycle): actual cumulative dose divided by the number of cycles initiated.
- Relative dose intensity (%): 100 \* ratio of actual cumulative dose and planned cumulative dose.

TPL N°: eTPL SA-02-01 TPL Version: 02

<sup>a13= 2 weeks - 1 day taken into account in the +1

b 6= 1 week - 1 day taken into account in the +1

• Planned cumulative dose (mg) – only used for calculation of relative dose intensity: Allocated dose level \* weight in kg \* number of cycles initiated. For subjects whose body mass index (BMI) is greater than 30 kg/m2, the formula should use a weight that, based on the subject's height, corresponds to a maximum BMI of 30. When a cycle is missed/skipped, this cycle is also included to count the number of cycles initiated.

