1 VISIT SCHEDULE

1.1 Dose Escalation Part

In the dose escalation part, up to 2 dose regimens may be evaluated:

- The Biweekly Regimen: patients are dosed once every 14 days (Q2W).
- The Priming Regimen: in the first cycle, patients receive a priming dose. After 14 days and thereafter, they are dosed with the maximum starting dose once every 14 days (Priming/Q2W).

An overview of the dosing frequency as well as treatment cycle duration and dose limiting toxicity (DLT) period duration, and scanning frequency is shown in Figure 1-1. A cycle is always 14 days and the DLT period is always 28 days, irrespective of which dose regimen the patients are following.

Further details on when the 2 dose regimens will be available and open for enrollment are described in Section 4.2.

Table 1-1 lists all of the assessments in the dose escalation part and indicates with an "X" the visits at which they are performed. All data obtained from these assessments must be supported in the patient's source documentation.

Table 1-2 shows the timing of the ECG assessments, Table 1-3 shows the timing of the PK sampling, Table 1-4 shows the timing of cytokine and complement sampling, and Table 1-5 shows the timing for measurement of vital signs in relation to infusions.

*: Mandatory PET-CT scans must be taken at screening and, if avid at screening, also at Cycle 2 Day 2, and week 12 (±7 days). If PET-CT at screening showed no avidity, a CT scan has to be done instead of a PET-CT in week 12 (±7 days).

: A CT scan must be performed at Cycle 3, Day 8-14 after first dose. From week 18 (\pm 7 days) until week 50 after first dosing, CT scans must be performed every 6 weeks (\pm 7 days), and every 12 weeks (\pm 7 days) thereafter. Imaging assessments should follow calendar days and should not be adjusted for delays in cycle starts. *: Only if a patient, who has been exposed to GEN1029, did not have any PET-CT scans while on treatment and displayed avidity at screening.

Figure 1-1 Overview of Dosing and Scanning Frequency, DLT and Cycle Duration – Dose Escalation Part

Treatment Cycle	Screening	Cycle 1-3 ¹			Cycle 4-PD ¹ End of treatment ²		Safety Follow-up ²¹		Patient follow-up	End of trial	Unscheduled		
Day	≤21 days prior to Visit C1-D1	1d	2d	3d ^{24,28}	8d	1d	8d ²²	-	30 days after last dosing	70 days after last dosing	13W, 26W, 39W + 52W after last dosing	-	-
Visit window ³		±1d	-	-	±1d	±3d	±1d	-	±7d	±7d	±14d	-	-
Informed Consent ⁴	Х												
Eligibility Criteria	Х												

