11.3 Treatments

The Safety Set will be used for the analyses below. Categorical data will be summarized as frequencies and percentages. For continuous data, mean, standard deviation, median, 25th and 75th percentiles, minimum, and maximum will be presented.

The duration of exposure in months to GEN1029 as well as the dose intensity (computed as the ratio of actual cumulative dose received and actual duration of exposure) will be summarized by means of descriptive statistics using the safety set.

Concomitant medications and significant non-drug therapies prior to and after the start of the IMP will be listed and summarized according to the anatomical therapeutic chemical (ATC) classification system, by dose cohort.

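### SAP dose intensity counts cycles instead of time, so a delay not recorded as a skipped cycle lowers neither dose intensity nor relative dose intensity, and this change from the protocol is not declared

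*SAP*

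**What the plan says.** - **Protocol 11.3** has dose intensity "computed as the ratio of actual cumulative dose received and actual duration of exposure". It does not define a relative dose intensity.
- **SAP 4.6** has dose intensity in mg per cycle, as "actual cumulative dose divided by the number of cycles initiated". RDI is 100 times the "ratio of actual cumulative dose and planned cumulative dose".
- **The planned cumulative dose**, which is "only used for calculation of relative dose intensity", is "Allocated dose level \* weight in kg \* number of cycles initiated". It contains no time term.
- **Skipped cycles** are covered in the same item: "When a cycle is missed/skipped, this cycle is also included to count the number of cycles initiated".
- **Treatment duration** is defined separately in SAP 4.6. For the Biweekly and Priming regimens it ends at the earliest of last dose plus 13 days, "last contact date, cut-off date".
- **SAP 17.2** reports RDI as a continuous variable and in five categories, with cut points at 110%, 90%, 70% and 50%.
- **SAP section 5** names three departures from the protocol: the dose-determining set, the PK set and the unused expansion part. Dose intensity is not among them.
- **Protocol 1.1**: "A cycle is always 14 days and the DLT period is always 28 days". Protocol 7.2.1.1 equates the maximum 14-day delay with one cycle.

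**The concern.** The two documents give different definitions of the same exposure measure, and the later one does not say that it departs from the earlier one. The change has a direction. When a cycle starts late but its dose is given in full, the dose total and the cycle count are the same as if it had been on time. Both SAP measures then ignore the delay, while the protocol's measure falls.

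Delay is a normal response to toxicity in this protocol. A first grade 2 liver elevation leads to a delay and a restart at the same level (Table 7-1). Grade 2 or 3 diarrhea leads to a hold with no reduction stated (Table 7-3). These are the two adverse events of special interest, and protocol 10.3 reports them in more than 50% and more than 40% of patients. A reader who uses RDI by dose level to judge whether a dose was delivered on schedule could be misled.

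**Working it through.** The documents state no dose-intensity figure, so there is none to reproduce. I applied both definitions to the same dosing histories.

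**Inputs.** The cycle length is 14 days (protocol 1.1). The SAP formulas and the count of skipped cycles come from SAP 4.6, and the reporting categories from SAP 17.2. My assumptions are that every dose is given in full at the allocated level and that weight is constant, so level and weight cancel.

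**Formulas.** Let D be full doses given, S cycles recorded as skipped, and T the days from first to last dose plus 14.

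- SAP RDI = 100 × D / (D + S)
- Per-time RDI = 100 × D / (T/14)

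| History, all doses full | T (days) | T/14 | Per-time RDI | SAP RDI, delays not coded as skips | SAP RDI, each delay coded as a skip |
|---|---|---|---|---|---|
| 4 doses, no delay | 56 | 4 | 100% | 100% | – |
| 2 doses, one 7-day delay | 35 | 2.5 | 80% | 100% | – |
| 4 doses, one 7-day delay | 63 | 4.5 | 89% | 100% | – |
| 4 doses, 7-day delay before each later dose | 3×21+14 = 77 | 5.5 | 4/5.5 = 73% | 4/4 = 100% | – |
| 4 doses, two 14-day delays | 14+28+28+14 = 84 | 6 | 4/6 = 67% | 4/4 = 100% | 4/(4+2) = 67% |

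The 7-day rows stay in the SAP's 90% to <110% category, whereas the per-time value falls in 70% to <90%. The last row falls in 90% to <110% or in 50% to <70%, depending only on how the delays were recorded.

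**Dose intensity itself.** For an illustrative 70 kg subject at 1.0 mg/kg, four doses total 280 mg. The SAP value is 280/4 = 70 mg per cycle with or without the three 7-day delays. Per time, it falls from 280/56 = 5.00 to 280/77 = 3.64 mg/day.

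**Delay followed by a reduction.** Take six doses with two 7-day delays, and halve doses 3 to 6. The halving is illustrative and not from the documents. The amount delivered is 2 + 4×0.5 = 4 dose-equivalents. SAP RDI is 4/6 = 67%. Per time, T = 98 days and 4/7 = 57%. The SAP figure drops, but only because of the reduction.

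**One dose per cycle.** The Intensified Regimen gives weekly doses for 8 weeks (SAP 3.2), which is two per 14-day cycle in cycles 1 to 4. A full cycle reads 2/1 = 200%. For Priming, if the allocated level is the full dose, a subject who receives exactly the planned lower priming dose reads below 100%.

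**Truncation.** If the SAP's treatment duration were used as the time base, a subject with one full dose and last contact on day 7 would have T = 7 and RDI = 1/(7/14) = 200%. Ending the window at last dose plus one interval gives 1/(14/14) = 100%.

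**The case against.** The strongest reply has four parts.

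1. **Skipped cycles count.** SAP 4.6 includes missed cycles in the denominator, and the protocol describes a 14-day delay as one cycle. If such delays are recorded as skips, the SAP figure equals the per-time figure. This stands for one-cycle delays, provided they are recorded that way. It does nothing for shorter delays, and no rule settles the recording.
2. **Repeat liver events lead to reductions.** In Table 7-1 a second grade 2 elevation, or a first grade 3 elevation, restarts at a reduced level. Protocol 7.2.1.1 also lowers the dose after a repeat grade 3 event of the DLT type. RDI then falls below 100%. This stands, although the delay still adds nothing to the fall. Full-dose delays remain possible after a first grade 2 liver event and after diarrhea holds.
3. **Delays are visible elsewhere.** Protocol 10.2.12 records a treatment postponed because of an adverse event as an interruption. SAP Tables 14.03.12.01 to 14.03.12.04 tabulate these events, Listing 16.02.03.02 shows interruptions by subject, and SAP 17.2 summarises treatment duration and dose reductions. This stands and limits the harm.
4. **Only dose intensity contradicts the protocol.** RDI has no protocol definition, so basing it on cycles is an analysis choice. This also stands.

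A reader might infer that RDI will read 100% in any repeatedly delayed subject, or that the exposure outputs cannot show whether a dose was deliverable. Points 1 to 3 show that the documents support neither inference.

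**Conclusion.** The concern holds in a limited form. The SAP replaces a per-time dose intensity with a per-cycle one, does not declare it, and carries the cycle count into RDI. Delays not recorded as skipped cycles lower neither measure. In the worked histories the gap is 11 to 33 percentage points (100% against 89% to 67%), enough to change the reporting category. For one-cycle delays the result turns on a recording choice that neither document governs.

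These sizes assume full doses and constant weight. They illustrate the rule and do not predict the trial's data, because the documents do not give the frequency of full-dose delays.

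The 200% reading is arithmetically right but reaches few records. SAP 4.5 puts the Intensified and Priming regimens in listings only, and SAP 3.3 counts three subjects in the first and one analysed in the second. It would be wrong to read it as distorting the dose-level summaries. DLT counts and the MTD do not use dose intensity. This is a descriptive exposure summary that should be corrected, and no primary conclusion depends on it.

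**What to change.** In SAP 4.6:

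- Define dose intensity as actual cumulative dose divided by time, as in protocol 11.3.
- Define RDI as actual cumulative dose over the dose scheduled under the subject's own regimen, from first dose to last dose plus one dosing interval. That means two doses per cycle for Intensified cycles 1 to 4, and the priming dose in cycle 1 for Priming.
- Do not truncate this window at last contact or cut-off. The existing treatment-duration variable cannot serve as the denominator unchanged.

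Delays then count the same whether they are recorded as delays or skips, so no delay-versus-skip rule is needed for this measure. A hold that ends in discontinuation still falls outside the window and has to be read from the interruption and discontinuation tables.

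If the sponsor prefers the per-cycle version, the minimum is to declare it in SAP section 5 and state when a delay is recorded as a skipped cycle. That removes the ambiguity but still leaves shorter delays uncounted.

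The cost is one derivation and its wording. Reported intensities become somewhat lower where doses were delayed.
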